### **Diuretics**

Co-administration of IMP with loop and thiazide diuretics might lead to clinically significant volume depletion.

Modifications to the dose of the loop and/or thiazide diuretic might be necessary. The Investigator should consult with relevant experts (e.g., nephrologists) as appropriate. For patients with a systolic blood pressure  $< 110$  mm Hg at Randomization, the doses of any diuretic or other antihypertensive medication may be decreased in order to prevent possible hypotension.

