### 10.2 SAFETY

Assessments for safety include AEs, clinical laboratory assessments, physical examination, ECG, weight and vital signs. An independent DMC will meet on a regular basis to review accumulating clinical trial safety data. Enrollment in Cohort 2 will only proceed following review of cases in Cohort 1 by the DMC, and similarly enrollment in Cohort 3 will only proceed following review of cases in Cohort 2 by the DMC.

Serum creatinine will be assessed at Baseline (Day 1, Visit 1) and on-site Visits 2, 3 and 4 (in cohort 3 on-site visit 4 was eliminated precluding any serum collection). A central laboratory will analyze samples and estimate change from Baseline in serum creatinine and eGFR. Renal safety will also be assessed on a regular basis by an independent expert, who may also be a member of the DMC.

The following safety endpoints will be assessed:

- Adverse events, AEs leading to discontinuation from the IMP, adverse events of special interest (AESIs), Events of Special Interest (EOSIs), SAEs and deaths
- Hypoglycemia (severe, documented symptomatic, or asymptomatic)
- Clinical laboratory results, vital signs and ECG results

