#### 11.2.4 Events of Special Interest (EOSIs)

An EOSI is a serious or non-serious AE of scientific and medical concern specific to the Sponsor’s product or program, for which ongoing monitoring may be appropriate. Such events may require further investigation in order to characterize and understand them. These events should be reported on the specific e-CRF page and will only qualify for expedited reporting when serious (fulfilling SAE criteria).

The EOSIs for this study are:

4. MACE (cardiovascular death, myocardial infarction, or stroke) and other specific CV events (eg, heart failure leading to hospitalization).
5. Severe hypoglycemia (see [Section 11.5.1.1](#))
6. Venous thrombotic events (including venous thrombosis deep and pulmonary embolism)
7. Pancreatitis
8. Fracture bone
9. AEs leading to amputations
10. Diabetic Ketoacidosis (DKA)
11. Malignancies of special interest (breast, bladder, renal cell, Leydig cell tumor of the testis, pancreatic, prostate, and follicular thyroid cancer)
12. Genital mycotic infections (to include vulvovaginal candidiasis in females and candida balanitis in males)
13. Urinary tract infection
14. Diarrhea

15. Volume depletion with serious consequence (orthostatic hypotension, orthostatic collapse fall, fracture)
16. Renal events, to include 50% decline in eGFR, end stage renal failure, renal death defined as eGFR < 15 ml/min/1.73m^2

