### **11.3 OBLIGATION OF THE INVESTIGATOR REGARDING SAFETY REPORTING**

#### **11.3.1 General guidelines for reporting adverse events**

All AEs, regardless of seriousness or relationship to IMP/NIMP, spanning from the signature of the informed consent form until the end of the study as defined by the protocol, are to be recorded on the corresponding page(s) or screen(s) of the case report form for included patients. Whenever possible, diagnosis or single syndrome should be reported instead of symptoms. The Investigator should specify the date of onset, intensity (see definitions in [Section 11.2.1](#)), action taken with respect to IMP/NIMP, corrective treatment/therapy given, additional investigations performed (eg, in the case of dermatologic lesions photographs are required), outcome, and Investigator's opinion as to whether there is a reasonable possibility that the AE was caused by the IMP/NIMP.

In this study, the use of concomitant medication, as well as the nature of the disease and comorbidities, might make it difficult to assess causal relationships, as might for example be the case with renal function or shifts in blood pressure. In such cases, where the nature of the relationship cannot be determined by the investigator, the Global Safety Officer with input from other appropriate study team members and/or DMC will determine if there is a causal relationship.

In order to ensure the safety of the patients, the Investigator should take appropriate measures to follow all AEs until clinical recovery is complete and laboratory results have returned to normal, or until progression has been stabilized, or until death. This may imply that observations will continue beyond the last planned visit per protocol, and that additional investigations may be requested by the monitoring team.

When treatment is prematurely discontinued, patients are to be assessed using the procedure planned for the end-of-study visit, including a pharmacokinetic sample if appropriate as defined by the protocol.

Laboratory, vital signs, or ECG abnormalities are to be recorded as AEs in the eCRF only if:

- symptomatic, and/or
- requiring either corrective treatment or consultation, and/or
- leading to IMP/NIMP discontinuation or modification of dosing, and/or
- fulfilling a seriousness criterion, and/or
- defined as an AESI.

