2.7.1.2 Treatment-emergent adverse events

The following TEAEs summaries will be provided by treatment for the safety population:

- Overview of TEAEs: number and percentage of patients with any TEAE, any TEAE of special interest, any severe TEAEs, any serious TEAE, any TEAE leading to death (if any occurred), and any TEAE leading to permanent treatment discontinuation.
- Summary of TEAEs by primary SOC and PT:
 - number and percentage of patients with at least one TEAE;
 - number of occurrences of TEAEs.

Patients presenting TEAEs will be listed sorted by treatment group primary SOC and PT.

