2.7.1.5 Adverse events of special interest

Adverse event of special interests (AESI) for this study are defined as follows:

- Pregnancy occurring in a female patient included in the clinical trial or in a female partner of a male patient entered in the clinical trial. It will be qualified as an SAE only if it fulfills one of the seriousness criteria.
 - In the event of pregnancy in a female patient, IMP should be discontinued,
 - Follow-up of the pregnancy in a female patient or in a female partner of a male patient is mandatory until the outcome has been determined.

- Symptomatic overdose (serious or nonserious) with IMP/non investigational medicinal product (NIMP)
 - A symptomatic overdose (accidental or intentional) with the IMP/NIMP is an event suspected by the Investigator or spontaneously notified by the patient and resulting in clinical symptoms and/or signs accompanied by administration of more than twice the intended daily dose within a 24-hour period. It will be recorded in the e-CRF as an AESI with immediate notification “Symptomatic OVERDOSE (accidental or intentional)” in all cases and will be qualified as an SAE only if it fulfills the SAE criteria.

(Please note that an Asymptomatic overdose with the IMP/NIMP, accidental or intentional, defined as administration of more than twice the intended daily dose within a 24-hour period, without clinical symptoms and/or signs, either suspected by the Investigator or spontaneously notified by the patient, not based on accountability assessment. It will be recorded as an AE “Asymptomatic OVERDOSE, accidental or intentional.”)

- ALT increased > 3X ULN

A summary of TEAEs reported as AESI (number and percentage of patients and the number of events) will be provided by AESI category and PT, sorted by decreasing incidence of PT within each AESI category.

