At least grade 2	>220 ms and increase from baseline $\geq 25\%$	
At least grade 3	>240 ms and increase from baseline $\geq 25\%$	
QRS		
High, all grades	>110 ms	Birth/0 to 27 days old : ≥ 85 ms 28 days/1 month to 23 months old: ≥ 85 ms 24 months/2 years to <6 years old: ≥ 95 ms 6 to <12 years old : ≥ 100 ms 12 to 16/18 years old : ≥ 110 ms
At least grade 1 (adults)	>110 ms	
At least grade 2 (adults)	>120 ms	
High and increase from baseline (adults)		
At least grade 1	>110 ms and increase from baseline $\geq 25\%$	
At least grade 2	>120 ms and increase from baseline $\geq 25\%$	
QTc Fridericia		
Increase from baseline, Grade 1	Increase from baseline [30-60] ms	All age classes: Increase from baseline (30-60] ms
Increase from baseline, Grade 2	Increase from baseline >60 ms	All age classes: Increase from baseline >60 ms

References:

- for adults: Criteria for Potentially Significant Abnormalities – for Phase 2/3 studies (oncology excepted) - Version 3.0 - 21-MAY-2014

- for children: Criteria for Potentially Clinically Significant Abnormalities for Studies in Children - Version 3.0 - 21-MAY-2014

Vital signs parameter	Adults	Children
PCSA criteria n/N1 (%)		
Systolic blood pressure supine		
Low and decrease from baseline	≤95 mmHg and decrease from baseline ≥20 mmHg	Birth/0 to 27 days old : ≤ 60 mmHg and decrease from baseline ≥20 mmHg 28 days/1 month to 23 months old: ≤ 70 mmHg and decrease from baseline ≥20 mmHg 24 months/2 years to <6 years old: ≤ 70 mmHg and decrease from baseline ≥20 mmHg 6 to <12 years old : ≤ 80 mmHg and decrease from baseline ≥20 mmHg 12 to 16/18 years old : ≤ 90 mmHg and decrease from baseline ≥20 mmHg
High and increase from baseline	≥160 mmHg and increase from baseline ≥20 mmHg	Birth/0 to 27 days old : ≥ 85 mmHg and increase from baseline ≥20 mmHg 28 days/1 month to 23 months old: ≥ 98 mmHg and increase from baseline ≥20 mmHg 24 months/2 years to <6 years old: ≥ 101 mmHg and increase from baseline ≥20 mmHg 6 to <12 years old : ≥ 108 mmHg and increase from baseline ≥20 mmHg 12 to 16/18 years old : ≥ 119 mmHg and increase from baseline ≥20 mmHg
Diastolic blood pressure supine		
Low and decrease from baseline	≤45 mmHg and decrease from baseline ≥10 mmHg	Birth/0 to <6 years old : ≤ 34 mmHg and decrease from baseline ≥10 mmHg 6 to <12 years old : ≤ 48 mmHg and decrease from baseline ≥10 mmHg 12 to 16/18 years old : ≤ 54 mmHg and decrease from baseline ≥10 mmHg

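### No planned table counts events of special interest by arm, or patients with any volume-depletion adverse event, although the protocol names that risk

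*Protocol*

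**What the plan says.** **The risk.** Protocol 9.8 (Diuretics) states: "Co-administration of IMP with loop and thiazide diuretics might lead to clinically significant volume depletion". Inclusion criterion I 07 requires oral diuretic treatment to have been prescribed or given, so the warning is relevant to the whole trial population.

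**The definition.** Protocol 11.2.4 opens broadly: "An EOSI is a serious or non-serious AE of scientific and medical concern". Item 15 then narrows this harm: "Volume depletion with serious consequence (orthostatic hypotension, orthostatic collapse fall, fracture". Items 12 to 14 (genital mycotic infection, urinary tract infection, diarrhea) carry no such limit.

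**The endpoint.** Protocol 10.2 lists among the safety endpoints: "Adverse events, AEs leading to discontinuation from the IMP, adverse events of special interest (AESIs), Events of Special Interest (EOSIs), SAEs and deaths". The clinical trial summary also names EOSIs under the primary safety endpoints.

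**The tables.** Protocol 14.8.1 and SAP 2.7.1 plan an overview, a "Summary of TEAEs by primary SOC and PT", several listings, and one grouped summary, for AESIs, which "will be provided by AESI category and PT". The AESIs are pregnancy, symptomatic overdose and ALT increase. Neither section plans an EOSI summary or defines a grouped volume-depletion or hypotension category.

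**The concern.** Safety and tolerability is the primary objective, and change in plasma volume is co-primary. Excess volume loss is the harm side of the intended effect, so a reader of the study report will want to know how many patients per arm had it.

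The planned tables do not answer that. A preferred-term table gives a separate row to each term, so dehydration, hypotension and near-syncope would appear as small separate counts. Rows cannot be added without knowing which patients appear in more than one, and a system organ class total also includes unrelated events. The one category that might have gathered these events, item 15, is restricted and has no planned table. Any grouping would then be chosen after unblinding, which a SAP is meant to prevent.

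**Working it through.** The plan gives no event rate or count for this harm, so there is no document figure to reproduce. The check has two parts.

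**1. Which planned outputs bear on volume depletion?**

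| Planned output | Where | Patients per arm with any volume-depletion AE? |
|---|---|---|
| TEAE overview | SAP 2.7.1.2 | No; any, special interest, severe, serious, fatal, leading to discontinuation |
| TEAEs by class and term | SAP 2.7.1.2 | No; one row per term |
| AESI summary | SAP 2.7.1.5 | No; three unrelated categories |
| EOSI summary | not planned | – |
| Low systolic pressure, abnormality count | SAP 2.7.3, Appendix C | No; a measurement |
| Standing minus sitting/supine pressure | SAP 2.7.3 | No; a measurement |
| Creatinine rise of 30% or more | Appendix C | No; a renal marker |
| Percent change in body weight | SAP 2.7.3 | No; a measurement |

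The low systolic criterion is "≤95 mmHg and decrease from baseline ≥20 mmHg". Both conditions must hold. Entry requires systolic pressure of at least 100 mmHg, so a patient starting at 105 mmHg is flagged only at 105 − 20 = 85 mmHg or below. In the other direction, Protocol 11.3.1 limits when a measurement becomes an adverse event: "Laboratory, vital signs, or ECG abnormalities are to be recorded as AEs in the eCRF only if" it is symptomatic, needs treatment or consultation, changes or stops treatment, is serious, or is an AESI. Measurements and adverse events therefore capture different patients.

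**2. What does grouping gain?**

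Inputs:
- 27 patients on 400 mg and 27 on placebo: Protocol Table 1 totals.
- Assumed: 25% vs 10% of patients with any such event (range 20% to 30% on 400 mg), spread evenly over five preferred terms.
- Signal: at least 3 more patients on 400 mg than on placebo.

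Formulas, with X ~ Bin(27, p₁) and Y ~ Bin(27, p₀):
- Grouped: G = P(X − Y ≥ 3), summed over all pairs of counts.
- One given term: q = the same sum with p₁/5 and p₀/5.
- Any of five terms, treated as independent: 1 − (1 − q)⁵.

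At 25% vs 10%, the expected grouped counts are 27 × 0.25 = 6.75 and 27 × 0.10 = 2.7. For one term they are 27 × 0.05 = 1.35 and 27 × 0.02 = 0.54. Then G = 0.714, q = 0.102, and any of five = 1 − 0.898⁵ = 0.416.

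| Assumed rates | Grouped | Any of five terms | One given term |
|---|---|---|---|
| 20% vs 10% | 53% | 27% | 6% |
| 25% vs 10% | 71% | 42% | 10% |
| 30% vs 10% | 85% | 56% | 15% |
| 10% vs 10% (no effect) | 12% | 5% | 1% |

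The first two probability columns are the fair comparison, because a reader sees all five rows. If each patient has at most one term, simulation gives 27%, 43% and 59% in place of 27%, 42% and 56%.

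Fewer or less even terms narrow the gain. With three equal terms q = 0.239, and any of three is 1 − 0.761³ = 0.56. If 60% of events fall on one term (15% vs 6%), that term alone reaches 48%.

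Precision: at 25% vs 10%, the half-width of a 95% interval is 1.96 × √(0.25 × 0.75/27 + 0.10 × 0.90/27) ≈ 0.20. The interval for the 15-point difference runs from about −5 to +35 points.

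**The case against.** **Much of the harm is measured.** Low systolic pressure is counted by arm, orthostatic change is analysed, home pressure is recorded daily in triplicate, creatinine rises are flagged, and plasma volume and total body water are themselves endpoints. All adverse events are recorded whatever their seriousness. Protocol 11.3.1 asks for a diagnosis or single syndrome rather than symptoms, which limits splitting. The DMC reviews safety after cohorts 1 and 2. This stands: a reader might infer that excess volume loss goes unobserved, and the documents do not support that. None of these outputs is a by-arm count of patients with the adverse event, however, and cohort 3 has only one site visit between Day 1 and Day 14.

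**Item 15 is wider than it looks.** Its bracket names orthostatic hypotension, and an EOSI may be non-serious, so a non-serious orthostatic hypotension event can arguably be reported. This also stands. A reader might infer that ordinary hypotension is always left out; the wording does not establish that. What it leaves unclear is whether 'serious' means the SAE criteria.

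**The wording of item 15 is not the main fault.** A reader might infer that the restriction would produce a special-interest count near zero, and that rewording it would cure the problem. Neither follows: no EOSI count is planned, so rewording alone adds no number.

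**The study is exploratory and small, and every event is listed.** Grouping from listings of about 64 patients is feasible. That is true, but it would not be prespecified.

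**The terms may share a system organ class.** The documents do not say how the terms are distributed over classes, so the point does not rest on that.

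**Conclusion.** The point holds as a gap in reporting. A named safety endpoint has no planned summary, and a risk named in the protocol has no planned count of affected patients per arm. No planned analysis becomes wrong, and the underlying adverse events are collected.

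The size is moderate. Under the assumed rates, grouping raises the chance of seeing an excess of at least 3 patients from 27–56% to 53–85%, about 1.5 to 2 times. Comparing the group with one preselected term (71% vs 10%) invites a much larger claim, but it ignores that all rows are visible. Grouping also raises the false-signal chance under this rule from 5% to 12%, and the interval is wide, so the count needs its confidence interval and would not by itself show a clear excess.

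The missing tables follow from the text alone. The percentages rest on assumed event rates, an even five-way split, independence between terms, and the approximate arm sizes of 27 and 27, which combine patients across cohorts.

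**What to change.** In SAP 2.7.1:

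1. Add a by-treatment table of EOSIs by category: number and percentage of patients, and number of events.
2. Add a grouped volume-depletion category of treatment-emergent events, serious or non-serious, defined by a preferred-term list fixed before unblinding (for example dehydration, hypovolemia, hypotension, orthostatic hypotension, presyncope, syncope, postural dizziness). Report the number and percentage of patients with at least one event, and a confidence interval for 400 mg minus placebo.
3. Show the events that meet the present item 15 wording as a subset.

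In Protocol 11.2.4, align item 15 with this category for data capture and state what 'serious' means there.

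The cost is one term list, two tables from data already collected, and one clarified line. No visit, sample or treatment rule changes. The drawback is that the group will also pick up some hypotension or dizziness caused by the heart failure itself; the placebo arm and the subset in step 3 help the reader to judge that.

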### **11.3 OBLIGATION OF THE INVESTIGATOR REGARDING SAFETY REPORTING**

#### **11.3.1 General guidelines for reporting adverse events**

All AEs, regardless of seriousness or relationship to IMP/NIMP, spanning from the signature of the informed consent form until the end of the study as defined by the protocol, are to be recorded on the corresponding page(s) or screen(s) of the case report form for included patients. Whenever possible, diagnosis or single syndrome should be reported instead of symptoms. The Investigator should specify the date of onset, intensity (see definitions in [Section 11.2.1](#)), action taken with respect to IMP/NIMP, corrective treatment/therapy given, additional investigations performed (eg, in the case of dermatologic lesions photographs are required), outcome, and Investigator's opinion as to whether there is a reasonable possibility that the AE was caused by the IMP/NIMP.

In this study, the use of concomitant medication, as well as the nature of the disease and comorbidities, might make it difficult to assess causal relationships, as might for example be the case with renal function or shifts in blood pressure. In such cases, where the nature of the relationship cannot be determined by the investigator, the Global Safety Officer with input from other appropriate study team members and/or DMC will determine if there is a causal relationship.

In order to ensure the safety of the patients, the Investigator should take appropriate measures to follow all AEs until clinical recovery is complete and laboratory results have returned to normal, or until progression has been stabilized, or until death. This may imply that observations will continue beyond the last planned visit per protocol, and that additional investigations may be requested by the monitoring team.

When treatment is prematurely discontinued, patients are to be assessed using the procedure planned for the end-of-study visit, including a pharmacokinetic sample if appropriate as defined by the protocol.

Laboratory, vital signs, or ECG abnormalities are to be recorded as AEs in the eCRF only if:

- symptomatic, and/or
- requiring either corrective treatment or consultation, and/or
- leading to IMP/NIMP discontinuation or modification of dosing, and/or
- fulfilling a seriousness criterion, and/or
- defined as an AESI.

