### 11.3.4 Guidelines for reporting events of special interest

If an EOSI fulfills the criteria of an SAE, reporting should be performed according to the instructions for reporting of SAEs (see [Section 11.3.2](#)). Otherwise, reporting should follow the instructions for an AE (see [Section 11.3.1](#)).

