2.7.5 Other related safety parameters

The HbA1c and eGFR parameters will be analysed descriptively by treatment group.

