Albumin		
Low (adults)	\leq 25 g/L	
Creatine Kinase		
High, all grades	> 3 ULN	\geq 3 ULN
At least grade 1 (adults)	> 3 ULN	
At least grade 2 (adults)	> 10 ULN	
Sodium		
Low	\leq 129 mmol/L	\leq 129 mmol/L
High	\geq 160 mmol/L	\geq 150 mmol/L
Potassium		
Low	< 3 mmol/L	Birth/0 to 27 days old : \leq 3.0 mmol/L 28 days/1 month to 16/18 years old : \leq 3.5 mmol/L
High	\geq 5.5 mmol/L	Birth/0 to 27 days old : \geq 7.0 mmol/L 28 days/1 month to 23 months old : \geq 6.0 mmol/L 24 months/2 years to 16/18 years old : \geq 5.5 mmol/L
Creatinine		
High	\geq 150 μ mol/L	Birth/0 to <6 years old : >53 μ mol/L 6 years to <12 years old: >90 μ mol/L 12 years to 16/18 years old: >132 μ mol/L

Laboratory parameter	Adults	Children
PCSA criteria n/N1 (%)		
Increase from baseline		
At least grade 1 (adults)	≥ 30% change from baseline	
At least grade 2 (adults)	≥ 100% change from baseline	
Creatinine Clearance		
Low, all grades	< 90 mL/min*	Birth/0 to 27 days old : < 25 ml/min/1.73m ² ** 28 days/1 month to 23 months old: < 45 ml/min/1.73m ² ** From 2 years old : < 60 ml/min/1.73m ² **
Mild (adults)	[60 – 90[mL/min*	
Moderate (adults)	[30 – 60[mL/min*	
Severe (adults)	[15 – 30[mL/min*	
End stage (adults)	< 15 mL/min*	
*MDRD or Cockcroft-Gault equation		**GFR Bedside Schwartz Formula Based on normal ranges: 20 to 50 (<8 days), 25 to 80 (8 days to 1 month), 30 to 90 (1-6 months), 40 to 115 (6-12 months), 60 to 190 (12-23 months), 90 to 165 (2-12 years), 80-120 (After 12 years)
BUN		
High	≥ 17 mmol/L	Birth/0 to 27 days old : ≥4.3 mmol/L 28 days/1 month to 16/18 years old: ≥6.4 mmol/L
Alanine Aminotransferase		
High, at least grade 1	> 3 ULN	≥ 3 ULN
High, at least grade 2	> 5 ULN	≥ 5 ULN
High, at least grade 3	> 10 ULN	≥ 10 ULN
High, at least grade 4	> 20 ULN	≥ 20 ULN
Aspartate Aminotransferase		
High, at least grade 1	> 3 ULN	≥ 3 ULN
High, at least grade 2	> 5 ULN	≥ 5 ULN
High, at least grade 3	> 10 ULN	≥ 10 ULN
High, at least grade 4	> 20 ULN	≥ 20 ULN

Laboratory parameter	Adults	Children
PCSA criteria n/N1 (%)		
Alkaline phosphatase		
High	> 1.5 ULN	≥ 1.5 ULN
Total Bilirubin		
High, all grades	> 1.5 ULN	≥ 1.3 ULN
At least grade 1 (adults)	> 1.5 ULN	
At least grade 2 (adults)	> 2 ULN	
Alanine Aminotransferase and tot bilirubin		
High	ALT > 3 ULN and TBILI > 2 ULN	ALT ≥ 3 ULN and TBILI ≥ 2 ULN
Direct bilirubin and total bilirubin		
High	BILDIR >35% TBILI and TBILI >1.5 ULN	BILDIR >35% TBILI and TBILI ≥ 1.3 ULN

References:

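### A non-serious 50% fall in eGFR, a named safety event, has conflicting recording rules in the protocol and no count in the SAP

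*Protocol*

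**What the plan says.** **The recording rule.** Protocol 11.3.1 states: "Laboratory, vital signs, or ECG abnormalities are to be recorded as AEs in the eCRF only if" at least one of five conditions is met. These are that the finding is symptomatic, "requiring either corrective treatment or consultation, and/or" that it leads to discontinuation or a dosing change, that it is serious, or that it is "defined as an AESI". The three AESIs in 11.2.3 are pregnancy, symptomatic overdose and raised ALT. None is renal.

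**The event.** Item 16 of the EOSI list in 11.2.4 reads "Renal events, to include 50% decline in eGFR", followed by end-stage renal failure and renal death. The same section describes an EOSI as a serious or non-serious AE and asks for it on a specific e-CRF page.

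**The routing.** Section 11.3.4 treats an EOSI that meets SAE criteria as an SAE. For the rest: "Otherwise, reporting should follow the instructions for an AE", with a reference back to 11.3.1.

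**The status of the event.** The Clinical Trial Summary lists EOSIs under the primary safety endpoint, and Protocol 10.2 lists them among the safety endpoints.

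**The analysis.** SAP 2.7.1.5 defines and tabulates AESIs only, and the SAP plans no EOSI summary. SAP 2.7.5 says: "The HbA1c and eGFR parameters will be analysed descriptively by treatment group". Appendix C flags creatinine at 150 µmol/L or more, at a rise of 30% or more (grade 1), and at "≥ 100% change from baseline" (grade 2). It also has creatinine-clearance classes.

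**The concern.** A 50% eGFR decline is a laboratory finding by definition, so it falls under the laboratory filter in 11.3.1. That filter names one special-interest class and omits the one to which this event belongs. Appendix B confirms that the list works as a strict filter: for neutropenia and thrombocytopenia it says an AE is recorded only when at least one 11.3.1 criterion is met.

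A site could reasonably read the protocol in two ways. Under 11.2.4 it fills in the EOSI page. Under 11.3.4 and 11.3.1 it may conclude that a silent, untreated fall is not to be recorded as an AE, and therefore that there is no EOSI to enter. The treatment-emergent AE tables would then depend on which section the site followed.

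This matters because Protocol 4.2.2 describes renal function in these patients as vulnerable and hard to assess for trends. The SAP also has no table that would show the number of such events by arm, however the sites reported them.

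**Working it through.** There is no figure in the plan to reproduce here. The check has two parts: the route the event takes, and what the SAP's cut-offs mean in terms of eGFR.

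**1. Route.** Take a patient whose eGFR halves, with no symptoms, no treatment, no consultation, no change in study drug and no seriousness criterion.
- 11.2.4: the event is EOSI 16, so the specific page applies.
- 11.3.4: it is not serious, so the AE instructions apply.
- 11.3.1: none of the first four conditions is met, and the fifth covers AESIs only. No AE record is required.

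The sections give different instructions for the same event.

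**2. Conversion.** Protocol 8.1 gives the MDRD equation with creatinine raised to the power −1.154. Within a patient the age, sex and race terms cancel (ignoring ageing over two weeks), so

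eGFR ratio = (creatinine ratio)^−1.154.

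| Criterion | Creatinine ratio | eGFR ratio | eGFR fall |
|---|---|---|---|
| SAP grade 1 (+30%) | 1.30 | 1.30^−1.154 = 0.739 | 26.1% |
| EOSI 16 | 2^(1/1.154) = 1.823 | 0.500 | 50.0% |
| SAP grade 2 (+100%) | 2.00 | 2.00^−1.154 = 0.449 | 55.1% |

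- The +30% limit catches every halving, because 1.823 exceeds 1.30. It also catches every fall from 26.1% upward.
- The +100% limit misses falls from 50% to just under 55.1%.

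**3. The other Appendix C limits.**
- *Absolute creatinine, 150 µmol/L.* A ratio of 1.823 stays below this limit when baseline is under 150 / 1.823 = 82.3 µmol/L. That is 0.93 mg/dL at an assumed 88.4 µmol/L per mg/dL. The limit is not specific either, since a patient can exceed it with little change from baseline.
- *Clearance classes (boundaries 90, 60, 30, 15).* Halving moves a patient to a worse class from any baseline between 30 and 180: for example 120 to 60, 60 to 30, 45 to 22.5. A small fall can do the same: 61 to 59 is 2 / 61 = 3.3%. Appendix C also leaves the equation open between MDRD and Cockcroft-Gault.

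**4. Illustration (assumed patient).** A 65-year-old non-black man has baseline creatinine 0.8 mg/dL, so eGFR = 186 × 0.8^−1.154 × 65^−0.203 = 103.1. Creatinine rises by a factor of 1.9 to 1.52 mg/dL (about 134 µmol/L). eGFR becomes 49.2, a fall of 52.3%. This meets EOSI 16 and the +30% limit, and he shifts to the moderate clearance class. He does not reach +100% or 150 µmol/L. Nothing in the output labels him as a renal EOSI.

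**5. Which samples count.** SAP 2.7.2 uses all post-baseline values in the treatment-emergent period for the abnormality counts, unplanned ones included. SAP 2.9 restricts post-baseline descriptive statistics to planned observations. A nadir found on an unscheduled sample would therefore be left out of a descriptive eGFR summary.

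**The case against.** Much can be said for the plan, and several stronger readings fail.

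**A reader might infer that the event is never recorded.** The documents do not support that. Section 11.2.4 asks for the specific page whether or not the event is serious. The 11.3.1 rule governs what is entered as an AE and does not define what an AE is. Protocol 11.5.1 shows that a special page without an AE entry is an accepted pattern: non-serious hypoglycemia is handled that way. Protocol 10.2 also has a central laboratory estimating change in creatinine and eGFR, so the value does not depend on site reporting. What remains is that 11.5.1 states its exception openly, whereas 11.3.4 tells sites to follow the AE instructions for EOSIs. The conflict is real even though the data exist.

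**A reader might infer that the SAP misses these patients.** It does not. Each one with a captured value in the treatment-emergent period meets the +30% criterion, is counted by treatment, and appears in the listing. SAP 2.9 also lists all individual data. The criterion is sensitive but not specific.

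**A reader might infer that rises between 82% and 99% appear only as grade 1 creatinine.** That is true of the change-from-baseline criteria alone. A rise from 1.2 to 2.2 mg/dL reaches about 194 µmol/L (assumed conversion 88.4) and so also crosses the 150 µmol/L limit.

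**The gap is narrow.** A consultation, treatment or study-drug discontinuation brings the event through the filter. Protocol 7.2.1 names a persistent fall of more than 50% as a possible reason to discontinue, and an independent renal expert reviews renal safety (10.2, 11.3.5). However, 7.2.1 is conditional: it says such cases might include a persistent decline without clinical improvement. The expert review is oversight and does not produce a tabulated result.

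**Conclusion.** The point holds as a conflict in recording instructions plus a missing prespecified count. A non-serious, asymptomatic, untreated 50% eGFR fall that leads to neither a consultation nor a study-drug change need not be recorded as an AE, and sites may handle it inconsistently. No planned table identifies it: the SAP's two creatinine change limits lie on either side of it, at eGFR falls of 26.1% and 55.1%.

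The event is recoverable from data already collected, so the loss is one of identification and consistency between sites. The conversion rests on the protocol's MDRD equation being used for eGFR at both time points.

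A reader might also infer that one or two missed events would change the renal conclusion. The documents give no event rate to support this. One patient in 27 (the planned size of the 400 mg and placebo groups) is 3.7 percentage points, which is simply the weight of any single patient. Creatinine and eGFR are summarised and listed in any case. The correction is still worth making, because EOSIs belong to the primary safety endpoint and the cost is very small.

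**What to change.** **Protocol.**
- In 11.3.1, add being defined as an EOSI as a further condition beside the AESI condition.
- Reconcile 11.2.4 and 11.3.4 with it, so that all three sections say the same about the specific page and the AE entry. The existing hypoglycemia exception in 11.5.1 should be stated where it applies to severe hypoglycemia, which is also an EOSI.

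**SAP.**
- Add a table of EOSIs by treatment group.
- In 2.7.5 and Appendix C, add the number of patients in each arm with an eGFR decline of at least 50% from the Day 1 baseline at any post-baseline sample. Derive it from central-laboratory values and include unscheduled samples.

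**Cost.** One added condition, aligned wording in two sections, and two tables. No new samples or visits are needed. The protocol change acts only on future reporting, and amendment 03 indicates that cohorts 1 and 2 were already under way or complete. The laboratory-derived count applies equally to all three cohorts and can be added to the SAP before database lock even if the protocol is left as it is.
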